### **2.3 Secondary Objectives**

- Operative duration
- Incidence of post-operative bleeding
- Incidence of readmission to haemorrhoidectomy/haemorrhoidoplasty related symptoms/condition (pain/pelvic symptoms/bleeding)
- Procedure-related complications (thrombosis, fistulation, incontinence, stenosis)
- Incidence and timing of recurrence of haemorrhoid-related symptoms
- Haemorrhoid-specific QoL questionnaire (Haemorrhoid Severity Score)

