## **1.2 Rationale and Justification for the Study**

We would be conducting a single-centre RCT simultaneously comparing the conventional open Milligan-Morgan haemorrhoidectomy (COH) and the laser haemorrhoidoplasty procedure (LAH) for the treatment of symptomatic grade II-IV haemorrhoids. Primary outcomes will be post-operative pain while secondary outcomes include post-operative bleeding, readmission and/or reoperations, haemorrhoid-related quality of life (QoL) results and recurrence of symptoms up to a year post procedure.

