## **7.4 Safety Monitoring Plan**

The Data Safety Monitoring Plan (DSMP) for this study can be divided into individual events and collated events.

Every individual complication will be evaluated by all members of the study team immediately after the event has occurred. The study team would review the case and its proceedings to determine whether the event was a direct result of the procedure or its technique, and whether this could have been prevented. The complication would also be scored for its severity based on the Clavien-Dindo Classification of Complications. If there is a severe complication, or if the complication is a direct result of the procedure or its technique, a technical pause would be called for in order to re-clarify the technical aspects as well as processes to avoid a repeat complication before the trial is resumed.

Interim analysis would also be carried out in a timely fashion (after 50% and 75% of the required sample size has been randomised). This would allow statistically significant differences in the outcome of the procedures to be identified. If one arm is grossly different from the other, the study team would convene to evaluate whether this outcome difference is regarded as a safety hazard to subsequent patients. If so, the trial would be halted or terminated prematurely.

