#### **b. Safety Analyses**

Every individual complication will be evaluated by all members of the study team immediately after the event has occurred. The study team would review the case and its proceedings to determine whether the event was a direct result of the procedure or its technique, and whether this could have been prevented. The complication would also be scored for its severity based on the Clavien-Dindo Classification of Complications. If there is a severe complication, or if the complication is a direct result of the procedure or its technique, a technical pause would be called for in order to re-clarify the technical aspects as well as processes to avoid a repeat complication before the trial is resumed.

c. Interim Analyses

Interim analysis would also be carried out in a timely fashion (after 50% and 75% of the required sample size has been randomised). This would allow statistically significant differences in the outcome of the procedures to be identified. If one arm is grossly different from the other, the study team would convene to evaluate whether this outcome difference is regarded as a safety hazard to subsequent patients. If so, the trial would be halted or terminated prematurely.

d. Describe the types of statistical interim analyses, including their timing.

Interim analysis would also be carried out in a timely fashion (after 50% and 75% of the required sample size has been randomised). This would allow statistically significant differences in the outcome of the procedures to be identified. If one arm is grossly different from the other, the study team would convene to evaluate whether this outcome difference is regarded as a safety hazard to subsequent patients. If so, the trial would be halted or terminated prematurely.

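### Section 2.3 limits readmissions and complications to procedure-related events, unlike 1.2 and 1.2.4, and names no blinded judge of relatedness

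*Protocol*

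**What the plan says.** Section 2.3 (Secondary Objectives) lists three harm outcomes that matter here:

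- Bleeding, with no condition attached: "Incidence of post-operative bleeding".
- Readmission, with a relatedness condition: "Incidence of readmission to haemorrhoidectomy/haemorrhoidoplasty related symptoms/condition (pain/pelvic symptoms/bleeding").
- Complications, with a relatedness condition: "Procedure-related complications (thrombosis, fistulation, incontinence, stenosis").

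Section 1.2, repeated in 1.2.4, describes the same family of outcomes differently: "secondary outcomes include post-operative bleeding, readmission and/or reoperations, haemorrhoid-related quality of life (QoL) results and recurrence of symptoms". Readmission carries no condition there, and reoperation, which 2.3 does not list, is included.

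Section 2.4.1 names operative risks. Pelvic sepsis appears for both procedures. Bowel injury and intestinal obstruction appear for LAH only.

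Sections 7.4 and 9.2 b describe how events are reviewed: "Every individual complication will be evaluated by all members of the study team immediately after the event has occurred". The team is to "determine whether the event was a direct result of the procedure or its technique", and each complication is graded by Clavien-Dindo. The stated consequence of a positive attribution is that "if the complication is a direct result of the procedure or its technique, a technical pause would be called for".

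Section 4 calls the trial double-blind and counts the procedurists among the study team's co-investigators. The patient is the only person that sections 4, 4.1 and 6.5 describe as blinded.

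**The concern.** A relatedness condition inside an endpoint definition means that someone must decide, case by case, whether an event enters the numerator. If that person knows the arm, the comparison can be shifted by opinion as well as by what happened to patients. Operating surgeons cannot be unaware of whether they excised or lasered. The protocol names neither a blinded judge nor, for readmissions, any judge at all.

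Two further weaknesses come with the same wording. The protocol gives two definitions of the readmission outcome, so an analyst could follow either. And if the four named complication types are read as a complete list, a serious harm that 2.4.1 lists only for LAH would fall outside the complication outcome.

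These are secondary outcomes, but they are what a reader would weigh against any pain benefit of LAH.

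**Working it through.** **The plan's own figure.** The only computed number is 64 per arm (9.1), for 50% v 25% with VAS above 7.5, 80% power, alpha 5% (taken as two-sided) and 10% loss.

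n = [1.960·√(2·0.375·0.625) + 0.842·√(0.25 + 0.1875)]² / 0.25² = (1.342 + 0.557)² / 0.0625 ≈ 57.7, so 58.

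Allowing for loss: 58 × 1.10 = 63.8, so 64; or 58 / 0.90 = 64.4, so 65. The figure reproduces. It does not concern the harm outcomes, and this point does not affect it.

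**The text side by side.**

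| Item | 2.3 | Elsewhere |
|---|---|---|
| Readmission | related only | no condition (1.2, 1.2.4) |
| Reoperation | not listed | listed (1.2, 1.2.4) |
| Bleeding | no condition | no condition (1.2, 1.2.4) |
| Complications | procedure-related; four types named | 2.4.1 adds pelvic sepsis (both arms), and bowel injury and obstruction (LAH) |
| Judge of relatedness | none named | study team, for complications, as a safety step (7.4, 9.2 b) |

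Section 7.2 also uses relatedness, but only to decide which serious events go to the review board.

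**Illustration 1: a false difference.** Assumptions: 64 per arm, the same true risk p in both arms, every event counted in one arm and a share k in the other, two-sided Fisher exact test at p<0.05 (the test and level in 9.2 a). With A ~ Bin(64, p) and B ~ Bin(64, kp), the probability is the sum of P(A=a)·P(B=b) over all a>b with Fisher p<0.05.

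| True risk p | k=1 (no filter) | k=0.90 | k=0.75 | k=0.60 |
|---|---|---|---|---|
| 3% | 0.2% | 0.2% | 0.3% | 0.4% |
| 5% | 0.6% | 0.8% | 1.2% | 1.9% |
| 10% | 1.2% | 1.8% | 3.5% | 6.5% |
| 15% | 1.4% | 2.5% | 5.5% | 11.7% |
| 30% | 1.5% | 3.7% | 11.5% | 28.4% |

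Both p and k are assumptions; the protocol supplies neither. Swapping the arms gives the same figures in the other direction.

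**Illustration 2: a hidden difference.** With assumed counts out of 64 per arm, 10 v 2 gives p=0.030 and 9 v 2 gives p=0.054; 13 v 4 gives p=0.035 and 12 v 4 gives p=0.059. Reclassifying one event is enough in each case. From 12 v 3 (p=0.025) it takes two, to 10 v 3 (p=0.076). Creating a difference from equal counts takes far more: all 6 of 6 (p=0.028), 8 of 10 (p=0.030) or 9 of 13 (p=0.035) in one arm.

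**The case against.** The strongest reply is that no section makes the study-team review decide what counts as an endpoint. Sections 7.4 and 9.2 b describe safety monitoring. Its input is every complication, its stated result is a technical pause, and the Clavien-Dindo grade is given whatever the attribution. This stands. A reader might infer that the unblinded surgeons decide the endpoint counts, but the text gives the review to all team members, limits it to complications and says nothing about who judges readmissions. What remains is a causal condition with no stated judge, beside a single attribution process that includes the operators.

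Second, the outcomes name symptoms or diagnoses, and a stenosis or a readmission for bleeding leaves little room for opinion. This stands in part: it makes large one-sided discarding unlikely. Pain and pelvic symptoms are broad, however, and the wording still asks that they be related.

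Third, a reader might infer that the whole harm comparison turns on attribution. It does not: bleeding, the one harm named in the hypothesis (2.1), is unconditional. Nor is ascertainment wholly open. Patients are told their arm only at 4-6 weeks, and late complications are sought by an administrator outside the randomisation process.

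Fourth, detailed adjudication rules may sit in a statistical analysis plan that is not shown. That is fair for the mechanics, but not for two conflicting definitions within the protocol.

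**Conclusion.** The point holds in a limited form. Section 2.3 conflicts with 1.2 and 1.2.4 on readmission and reoperation. Its complication list is narrower than the risks in 2.4.1. For readmissions and complications only, the relatedness condition leaves a route by which unblinded attribution could influence the counts.

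That such influence would occur, or in which direction, cannot be shown from the document. In the illustration its effect is negligible when events are rare or nearly all are kept: 1.9% at 5% risk even with 60% kept, and 3.7% at 30% risk with 90% kept. It becomes material (11.5% to 28.4%) only when events are common and a quarter or more are set aside in one arm. A real difference near the significance limit is more fragile, since one or two events can remove it. All of this rests on assumed risks, counts and shares kept. The case for change rests on the conflicting text and the low cost of settling it, not on a demonstrated bias.

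**What to change.** Reconcile 2.3 with 1.2 and 1.2.4, and align 9.2 b:

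- Compare, by randomised arm, all readmissions, all reoperations and all post-operative complications by Clavien-Dindo grade, whatever the attribution. The grading is already planned.
- Keep the procedure-related subset as a supporting, descriptive line.
- Ask about readmission to any hospital at the 4-6 week visit and at the 3-month and 1-year calls.

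Counting all complications also brings in the harms that 2.4.1 names and 2.3 omits. The safety review in 7.4 need not change.

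The cost is wording in two sections and one question at contacts already scheduled. The downside is that some unrelated events, readmissions up to one year in particular, will enter both arms and slightly dilute the comparison; the descriptive line shows how many.

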## **2.4 Potential Risks and Benefits:**

### **2.4.1 Potential Risks**

Risk of the participation in the trial include:

- Breach of patient confidentiality and personal data

Risk of General Anaesthesia for both procedures is in keeping with that of those patients not involved in the study. These includes but not limited to:

- Major adverse cardiac events (MACE)
- Cerebral vascular accidents (stroke)
- Barotrauma
- Damage or loss of dentition

Risk of Operation:

a. Conventional open haemorrhoidectomy (COH):

- i. Bleeding
- ii. Anal sphincter injury which may lead to fecal incontinence
- iii. Anal stenosis
- iv. Pelvic sepsis
- v. Recurrence of haemorrhoids

b. Laser haemorrhoidoplasty procedure (LAH):

- i. Bleeding
- ii. Thrombosis
- iii. Anal sphincter injury which may lead to fecal incontinence
- iv. Pelvic sepsis
- v. Bowel injury which may necessitate emergency surgery and/or stoma creation
- vi. Intestinal obstruction which may necessitate stoma creation

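### Secondary outcomes are inconsistent: Section 2.3 omits reoperation, named in 1.2 and 1.2.4, and its complication list leaves out three harms that 2.4.1 lists as risks

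*Protocol*

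**What the plan says.** The Protocol describes the secondary outcomes in more than one place.

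- Section 1.2 states that "secondary outcomes include post-operative bleeding, readmission and/or reoperations", among others, will be assessed. Section 1.2.4 repeats the sentence.
- Section 2.3, the formal list, has no reoperation item. Its clinical-event items are "Incidence of post-operative bleeding", "Incidence of readmission to haemorrhoidectomy/haemorrhoidoplasty related symptoms/condition (pain/pelvic symptoms/bleeding" in brackets, "Incidence and timing of recurrence of haemorrhoid-related symptoms", and the complication item "Procedure-related complications (thrombosis, fistulation, incontinence, stenosis", again in brackets.
- Section 2.4.1 lists the risks of each operation. Pelvic sepsis appears for both. Two items appear for LAH only: "Bowel injury which may necessitate emergency surgery and/or stoma creation" and "Intestinal obstruction which may necessitate stoma creation".
- Section 7.4, repeated in 9.2 under the safety analyses, has the study team review every complication and adds: "The complication would also be scored for its severity based on the Clavien-Dindo Classification of Complications". Section 7.4 also provides for collated review through interim analyses after 50% and 75% of the sample has been randomised, asking whether one arm differs grossly from the other.

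**The concern.** There are two separate problems.

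The first is a direct conflict. A reader of 1.2 and 1.2.4 takes reoperation to be a secondary outcome; a reader of 2.3 does not. Whoever builds the data sheet or the results tables from 2.3 has no instruction to include it.

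The second is a mismatch between the complication outcome and the Protocol's own risk list. The bracket in 2.3 names four conditions with no wording to show that they are examples. Pelvic sepsis is absent, although the rationale in 1.2.1 names it alongside bleeding as a complication of haemorrhoid treatment. Bowel injury and intestinal obstruction are absent too. They are the only items in 2.4.1 for which a stoma is mentioned, and both are listed for the new technique alone. Fistulation, by contrast, is in the outcome but is not a listed risk of either operation. The two lists appear not to have been reconciled.

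The introduction (1.1) cites fewer complications with LAH in preliminary studies as part of the reason for a direct comparison. A complication outcome that need not count the gravest risks listed for LAH would answer that question incompletely.

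**Working it through.** **Step 1. Set the risks in 2.4.1 against the outcomes in 2.3.** COH is the conventional open operation.

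| Event | COH risk in 2.4.1 | LAH risk in 2.4.1 | Named in 2.3 |
|---|---|---|---|
| Bleeding | yes | yes | yes, own item |
| Sphincter injury / incontinence | yes | yes | yes, complication item |
| Anal stenosis | yes | no | yes, complication item |
| Recurrence | yes | no | yes, own item |
| Thrombosis | no | yes | yes, complication item |
| Pelvic sepsis | yes | yes | no; in part through readmission for pelvic symptoms |
| Bowel injury | no | yes | no |
| Intestinal obstruction | no | yes | no |
| Fistulation | no | no | yes, complication item |

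Three listed risks have no named outcome: one belongs to both arms and two to LAH only. The readmission item could pick up pelvic sepsis that brings a patient back. It would not pick up sepsis during the index stay, nor a bowel injury recognised and treated in that stay.

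**Step 2. Set the secondary-outcome statements side by side.** Reoperation: present in 1.2, present in 1.2.4, absent from 2.3. Readmission does not stand in for it, since a patient can be reoperated on during the index stay, or readmitted without an operation.

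**Step 3. What a formal comparison could show.** The Protocol gives no rates for these harms, so the rates below are assumptions. The denominator is the planned 64 per arm (9.1). That figure reproduces: with 50% versus 25%, two-sided 5% alpha (sidedness is not stated), 80% power and pooled variance,

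n = [1.960·√(2·0.375·0.625) + 0.842·√(0.25 + 0.1875)]² / 0.25² = 57.7, so 58 per arm; 58 × 1.1 = 63.8, so 64.

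The chance of at least one event among 64 LAH patients is 1 − (1 − p)^64. Power is for Fisher's exact test, the test 9.2 sets for categorical data, with no events in the COH arm.

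| Assumed LAH rate p | Chance of at least one event | Power against 0 of 64 |
|---|---|---|
| 0.5% | 27% | not computed |
| 1% | 47% | about 0% |
| 2% | 73% | 0.2% |
| 5% | 96% | 10% |

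The threshold explains the low power: 5 of 64 against 0 of 64 gives p = 0.058, and 6 of 64 gives p = 0.028. If no event is seen in 64 patients, the one-sided 95% upper limit for the rate is 1 − 0.05^(1/64) = 4.6%.

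Naming these harms would therefore hardly alter a significance test. The gain is that any event that occurs is shown by arm.

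**The case against.** The strongest reply is that nothing goes unrecorded. Sections 7.4 and 9.2 cover every complication in either arm, without restriction to the four named in 2.3, and grade each one. Section 7.4 is not confined to case review and technical pauses: its collated part compares the arms at two interim looks, and 4.4.1 makes the number and severity of complications a ground for stopping. The bracket in 2.3 might also be meant as examples, and the data collection sheet, the separately attached questionnaire package or an analysis plan may hold fuller categories. Reoperation remains a stated outcome in two current sections. All of this stands, and it limits the point to the formal outcome list. It does not remove it. The interim text does not say which outcomes are compared, 9.2 describes no final between-arm tabulation of all graded complications, and documents not shown cannot settle which of two conflicting lists in the Protocol applies.

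A reader might go further and infer that the comparison is tilted towards LAH, since 3 of its 6 listed risks have no named outcome against 1 of 5 for COH. The documents do not support that. The counts are of disclosure items, not events, and no rates are given. Pelvic sepsis is a risk of both arms, so its omission has no stated direction, and it is partly covered by readmission. Thrombosis, listed for LAH only, is named in 2.3. Recurrence is listed as a risk for COH only, yet 2.3 measures it without limiting it to an arm, so the risk lists do not work as arm-specific outcome definitions.

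**Conclusion.** The point holds as an internal inconsistency in the secondary outcomes. The conflict over reoperation is the firmest part and needs no assumption. The complication part rests on reading the bracket in 2.3 as the definition of the outcome, which is how it is worded. On that reading pelvic sepsis, bowel injury and intestinal obstruction are graded for safety but sit outside the formal secondary complication outcome, and the serious harms listed only for LAH could be missing from the between-arm results.

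Neither the direction nor the size of any effect on the reported complication rates can be computed. With rates in the assumed range of 1% to 5%, a test would have at most about 10% power, so the consequence is incomplete reporting of harm rather than a changed test result. The primary pain outcome and the sample size are unaffected. The correction is worth making, but this is not a fatal flaw.

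**What to change.** Make two changes to Section 2.3, preferably before the first interim comparison.

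1. Reword the complication item as all procedure-related complications in each arm, reported by type and by the Clavien-Dindo grade already assigned under 7.4, including every risk listed in 2.4.1 (so pelvic sepsis, bowel injury and intestinal obstruction) together with the four conditions now named.
2. Add reoperation up to 1 year as a secondary outcome, to agree with 1.2 and 1.2.4. The 1-year horizon matches the last planned telephone interview.

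Report counts by arm even where they are too small to test, and do not read a non-significant Fisher test on these events as evidence that the arms are equally safe.

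The cost is Protocol wording, a few fields on the data collection sheet and some extra table rows. Grading is already planned for every complication, so no visit, patient or change to the sample size is needed.

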## **2.4 Potential Risks and Benefits:**

### **2.4.1 Potential Risks**

Risk of the participation in the trial include:

- Breach of patient confidentiality and personal data

Risk of General Anaesthesia for both procedures is in keeping with that of those patients not involved in the study. These includes but not limited to:

- Major adverse cardiac events (MACE)
- Cerebral vascular accidents (stroke)
- Barotrauma
- Damage or loss of dentition

Risk of Operation:

a. Conventional open haemorrhoidectomy (COH):

- i. Bleeding
- ii. Anal sphincter injury which may lead to fecal incontinence
- iii. Anal stenosis
- iv. Pelvic sepsis
- v. Recurrence of haemorrhoids

b. Laser haemorrhoidoplasty procedure (LAH):

- i. Bleeding
- ii. Thrombosis
- iii. Anal sphincter injury which may lead to fecal incontinence
- iv. Pelvic sepsis
- v. Bowel injury which may necessitate emergency surgery and/or stoma creation
- vi. Intestinal obstruction which may necessitate stoma creation

### **2.4.2 Potential Benefits**

The benefits of participation in this trial is that patients will be closely monitored post procedure for their pain and symptoms and will receive a phone calls outside the regular follow up period, up to a year post-procedure, to follow up on their haemorrhoid-related symptoms.

They will also potentially may receive a procedure that could potentially cause less pain and have a lower risk of post-operative bleeding.

## **3 STUDY POPULATION**

### **3.1 List the Number and Nature of Subjects to be Enrolled**

Based on previous studies, as well as unpublished results from surgeons who have performed LAH around the South East Asian region, we are expecting 50% of the patients in the COH arm to have a VAS score of more than 7.5. We expect to see 25% patients in the LAH arm having a VAS score of more than 7.5.

With a power of 80%, chance of type 1 error (alpha) less than 5% and accounting for 10% of loss to follow up rate, the sample size required for the study to be adequate powered is having 64 patients in

each arm (N=128).

### **3.2 Criteria for Recruitment and Recruitment Process**

Patients who are seen in the specialist outpatient clinics (SOC) or who are admitted for haemorrhoid-related symptoms/complications will be evaluated by one of the PI/co-PIs. All of them would need to have the usual clinical and endoscopic assessment of the colon to ascertain that the haemorrhoids are the only cause of their symptoms. They also should not have previous operation for haemorrhoids, excluding rubber band ligations. Only after the above would they be eligible for recruitment into the study.

